10.5.3. Laboratory Analyses

Clinical laboratory (eg, hematology and chemistry) values to be evaluated will be specified in the Statistical Analysis Plan and collected in the EDC system. Collected values may be a subset of all the values obtained in the requested sampling, eg, a complete blood count with differential may be requested for the evaluation of neutrophils only. Analyzed laboratory values that are abnormal will be flagged and identified as outside (above or below) the normal range.

Laboratory parameters that are graded in NCI-CTCAE Version 4.03 or higher will be summarized by NCI-CTCAE grade. Shift tables will be provided as appropriate.

10.5.4. Physical Examinations

Physical examination results collected in association with an AE will be listed and summarized.

10.5.5. Vital Signs

Specific vital signs (eg, blood pressure and temperature) will be summarized and listed. The change from baseline will also be presented.

10.5.6. Electrocardiograms

The percentage of patients with abnormal and clinically significant ECG findings will be presented.

10.6. Sample Size Consideration

This study is designed to provide adequate power for primary endpoints of ORR and PSA response rate. A sample size of approximately 100 patients is planned (at approximately 45 centers with a projected average enrollment of 2 to 3 patients per center).

Assuming ORR of 35% for pamiparib in CTC-HRD-positive patients versus 15% for historical control in patients with measurable disease, the study power is 88% using a binomial exact test and 1-sided type-I error of 0.025 with $n = 50$. The binomial exact 95% CI of 35% ORR is 22.1% to 49.8% with a sample size of 50 patients.

Assuming PSA response rate of 50% for pamiparib versus 30% for historical control in CTC-HRD-positive patients with or without measurable disease, a sample size of 80 patients in this population will provide 95% study power using a binomial exact test and 1-sided type-I error of 0.025. The binomial exact 95% CI of 50% response rate is 38.6% to 61.4% with $n = 80$.

To explore the efficacy of pamiparib in patients with CTC-HRD-negative, but BRCA1/2-mutant mCRPC with or without measurable disease, approximately 20 patients will be enrolled in these cohorts.

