10.2. Efficacy Analyses

10.2.1. Primary Efficacy Endpoint Analyses

The primary endpoints of the study include ORR by IRC assessment in CTC-HRD-positive patients with measurable disease and PSA response rate in CTC-HRD-positive patients with or without measurable disease per PCWG3 criteria.

ORR is defined as the proportion of patients with best objective response of CR or PR confirmed at a subsequent timepoint ≥ 4 weeks later by IRC assessment. Patients without tumor assessment are considered non-responders.

ORR is assumed as 35% for pamiparib and estimated as 15% for historical control in the study population. The null and alternative hypotheses are set as follows:

$$H_0: \text{ORR} = 15\%$$

$$H_a: \text{ORR} > 15\%$$

PSA response rate is defined as the proportion of patients with PSA decline $\geq 50\%$ from baseline (confirmed by a second PSA value ≥ 3 weeks later).

PSA response rate is assumed as 50% for pamiparib and estimated as 30% for historical control in the study population. The null and alternative hypotheses are set as follows:

$$H_0 : \text{ORR} = 30\%$$

$$H_a : \text{ORR} > 30\%$$

Binomial exact tests will be performed for above hypotheses in the Efficacy-Evaluable Analysis Set. Two-sided binomial exact 95% CI of response rate will be constructed to assess the precision of the estimates.

To control the overall study type-I error rate, ORR and PSA response rate will be tested sequentially. If the ORR test shows significance at 1-sided 0.025 significance level, PSA response rate will be tested at a 1-sided 0.025 significance level.

The primary efficacy analyses will be conducted when mature response data have been observed, which will be determined by the sponsor.

A sensitivity analysis of response rate will be conducted using the Safety Analysis Set.

ORR and PSA response rate will be summarized in the specified subgroups: age group (< 65 versus ≥ 65), race, geographic region, ECOG performance status, BRCA1/2-mutant status, and number of prior lines of therapy.

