#### **6.2.4 Multiplicity Adjustment**

To control the overall study type I error rate, the primary efficacy endpoint analyses for ORR and PSA response rate will be tested sequentially.

If the hypothesis test for ORR is statistically significant at a one-sided 0.025 level (ie, one-sided  $p\text{-value} < 0.025$ ), then the PSA response rate will be tested at a one-sided 0.025 significance level. If the primary endpoint of ORR is not statistically significant, the primary endpoint of PSA response rate will not be tested for statistical significance.

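### The 95% power stated for PSA response ignores the ORR gate; under the planned test order it is about 84–86% and cannot exceed 88%

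*Protocol*

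**What the plan says.** Protocol 10.6 gives a separate power figure for each primary endpoint. For ORR (35% against 15%, n = 50), "the study power is 88% using a binomial exact test and 1-sided type-I error of 0.025". For PSA response (50% against 30%, n = 80), "a sample size of 80 patients in this population will provide 95% study power using a binomial exact test", also at one-sided 0.025. The Synopsis and SAP 5 repeat both figures.

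The testing rule is stated elsewhere. Protocol 10.2.1: "To control the overall study type-I error rate, ORR and PSA response rate will be tested sequentially". SAP 6.2.4 spells out the consequence: "If the primary endpoint of ORR is not statistically significant, the primary endpoint of PSA response rate will not be tested for statistical significance". SAP 6.4.1 likewise rules out any significance claim for PSA when ORR fails.

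None of the three sample-size sections mentions this order, says whether 95% is marginal or conditional, or gives the probability of success on both endpoints.

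**The concern.** In a fixed sequence the second hypothesis can be rejected only if the first has been. Its power in the trial is the joint probability that both tests succeed, so it cannot be larger than the power of the first test. The plan gives 88% for the first and 95% for the second and uses the same term, study power, for both. The two figures cannot both describe what the trial delivers.

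A reader of the sample-size section would take PSA to be the safer of the two primary endpoints. Under the plan's own rule it cannot be more likely to succeed than ORR. The reader would also look for the risk in the 80-patient PSA sample, when most of it lies in the 50-patient ORR test.

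**Working it through.** **Inputs.** One-sided alpha 0.025 for each test, with PSA gated on ORR (Protocol 10.2.1, SAP 6.2.4). ORR 15% under the null and 35% under the alternative, n = 50; PSA 30% and 50%, n = 80 (Protocol 10.6). The 50 Cohort 1 patients enter both tests and the 30 Cohort 2 patients enter only the PSA test (Protocol 3.1). The documents give no within-patient association between objective response and PSA response, so it is an assumption here and is varied over its range.

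**Step 1: reproduce the plan's figures.** The critical value is the smallest r with P(X ≥ r | n, p0) ≤ 0.025. Power is P(X ≥ r | n, p1).

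| Test | Size at r − 1 | Critical value r | Size at r | Power | Plan says |
|---|---|---|---|---|---|
| ORR, n = 50 | 0.0301 (13) | 14 | 0.0132 | 0.8837 | 88% |
| PSA, n = 80 | 0.0360 (32) | 33 | 0.0211 | 0.9535 | 95% |

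Both figures reproduce, the PSA figure as the power of a test that ignores the gate.

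**Step 2: bounds that hold for any association.**

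- Ceiling: P(both) ≤ min(0.8837, 0.9535) = 0.8837.
- Floor: P(both) ≥ 0.8837 + 0.9535 − 1 = 0.8372.

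So 95% is out of reach under the plan's own assumptions.

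**Step 3: independent endpoints.** 0.8837 × 0.9535 = 0.8426.

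**Step 4: associated endpoints, exact.** Let φ be the correlation between the two responses within a Cohort 1 patient, with a PSA response rate of 50% in both cohorts. The probability of having both responses is

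p11 = 0.35 × 0.50 + φ √(0.35 × 0.65 × 0.50 × 0.50) = 0.175 + 0.2385 φ.

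It cannot exceed 0.35, so φ ≤ 0.175 / 0.2385 = 0.734. The joint power is

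Σ (x = 14 to 50) P(X = x | 50, 0.35) × P(A + B + C ≥ 33),

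where A ~ Bin(x, p11/0.35), B ~ Bin(50 − x, (0.50 − p11)/0.65) and C ~ Bin(30, 0.50) are independent.

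| φ | Probability that PSA is tested and significant |
|---|---|
| −0.3 | 83.9% |
| 0 | 84.3% |
| 0.3 | 84.8% |
| 0.5 | 85.3% |
| 0.7 | 86.0% |
| 0.734 (maximum) | 86.1% |

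**Step 5: where the risk lies.** With independence the chance of no PSA claim is 1 − 0.8426 = 0.1574. Of this, 1 − 0.8837 = 0.1163 is failure at the ORR gate, about three quarters of the total, and 0.1574 − 0.1163 = 0.0411 is failure of the PSA test after the gate opens. At the maximum φ the total is 1 − 0.8612 = 0.1388, with the same 0.1163 from the gate.

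**Interim rule.** These figures leave out the futility look (fewer than 6 PSA responses in the first 20 patients), because it is non-binding. If every such halt became permanent, the stand-alone PSA power would fall from 95.4% to 93.9%.

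**The case against.** The strongest reply is that no stated number is miscalculated. The 95% is exact for the test, sample size and rates that the sentence names. Reporting marginal power for each hypothesis in a fixed sequence is common. Under independence 95% is also the power of the PSA test given that it is carried out (0.8426 / 0.8837 = 95.4%). The 88% stands in the preceding paragraph, and the gate is disclosed in the analysis sections, so a careful reader can combine them. Joint power of 84–86% may still be called adequate. No sample size, cut-off or alpha level changes. Finally, SAP 8 records that the trial was terminated after 13 patients and that no efficacy analysis will be done, so neither test will be run.

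Much of this stands. It is an error of labelling and omission, type I error is untouched, and no reported result depends on it. It does not remove the point. The sentence says what the sample size will provide as study power, without calling the figure marginal or mentioning the gate, and the trial as designed provides less. Early termination does not correct the statement, and SAP 5 repeats it in the same document that records the termination. The reply is also right that the 84–86% range assumes a non-negative association, which should be said. The assumption matters little, since the floor under any association is 83.7%.

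**Conclusion.** The concern holds. The stated 95% is the stand-alone power of the PSA test. Under the planned sequence the power for PSA is 84.3% to 86.1% for independent to maximally positively associated responses, 83.7% at the lowest conceivable, and never above 88.4%. The plan overstates it by about 9 to 11 points (95 − 86.1 = 8.9; 95 − 84.3 = 10.7), and the risk of no PSA claim is roughly three times the 5% implied.

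This rests on the plan's own rates (ORR 35%, PSA 50%), full cohorts of 50 and 30, and no binding interim stop. The 88.4% ceiling applies at a true ORR of 35% and would move with that rate. The point concerns the design as planned.

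**What to change.** In Protocol 10.6, the Synopsis and SAP 5, describe 95% as the marginal power of the PSA test and add a sentence such as: *Because PSA response rate is tested only if ORR is significant, the probability of significance on both primary endpoints under the design assumptions is approximately 84–86%, assuming a non-negative association between objective and PSA response, and at most 88%.*

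The change is to text only. Sample size, critical values, alpha and test order stay as they are. The cost is a less favourable figure for the second primary endpoint.

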10.7. Interim Analysis

A non-binding interim futility analysis will be performed among the first 20 patients enrolled in Cohorts 1 and 2 (Table 2). If the confirmed PSA response rate is $< 30\%$ (< 6 responses), enrollment will be halted and safety and efficacy data will be further evaluated before making the decision of stopping enrollment permanently. The decision to continue the enrollment may be made at any time the 6 confirmed PSA responses in Cohorts 1 and 2 can be documented; enrollment of all 20 patients is not required before determining further patient accrual.

11. STUDY ADMINISTRATION AND INVESTIGATOR OBLIGATIONS

11.1. Regulatory Authority Approval

The sponsor will obtain approval to conduct the study from the appropriate regulatory agency in accordance with any applicable country-specific regulatory requirements or file the protocol to appropriate regulatory agency before the study is initiated at a study center in that country.

11.2. Investigator Responsibilities

11.2.1. Good Clinical Practice

The investigator will ensure that this study is conducted in accordance with the principles of the “Declaration of Helsinki” International Council for Harmonisation guidelines, and that the basic principles of “Good Clinical Practice,” as outlined in 21 Code of Federal Regulations 312, Subpart D, “Responsibilities of Sponsors and Investigators,” 21 Code of Federal Regulations, Part 50, and 21 Code of Federal Regulations, Part 56, are adhered to. In addition, this clinical study will be conducted

in the European Union according to Directive 2001/20/EC, until the application of Regulation EU No 536/2014, which will then be followed.

Investigators and all subinvestigators must provide documentation of their financial interest or arrangements with BeiGene or proprietary interests in the drug being studied. This documentation must be provided before the participation of the investigator and any subinvestigator. The investigator and subinvestigator agree to notify BeiGene or its authorized representative of any change in reportable interests during the study and for 1 year following completion of the study.

11.2.2. Ethical Conduct of the Study and Ethics Approval

This study will be conducted by the principal investigator and the study center in accordance with Good Clinical Practice and all applicable regulatory requirements, including, where applicable, the current version of the Declaration of Helsinki.

The investigator (or sponsor, where applicable) is responsible for ensuring that this protocol, the study center's ICF, and any other information that will be presented to potential patients (eg, advertisements or information that supports or supplements the ICF) are reviewed and approved by the appropriate IEC/IRB.

The IEC/IRB must be constituted in accordance with all applicable regulatory requirements. The sponsor will provide the investigator with relevant document(s)/data that are needed for IEC/IRB review and approval of the study.

Before pamiparib can be shipped to the study center, the sponsor or its authorized representative must receive copies of the IEC/IRB approval, the approved ICF, and any other information that the IEC/IRB has approved for presentation to potential patients.

If the protocol, the ICF, or any other information that the IEC/IRB has approved for presentation to potential patients is amended during the study, the investigator is responsible for ensuring the IEC/IRB reviews and approves, where applicable, these amended documents. The investigator must follow all applicable regulatory requirements pertaining to the use of an amended ICF including obtaining IEC/IRB approval of the amended form before new patient consent to take part in the study using this version of the form. Copies of the IEC/IRB approval of the amended ICF/other information, the approved amended ICF/other information and all related correspondence must be forwarded to the sponsor promptly.

11.2.3. Informed Consent

The investigator is responsible for obtaining written informed consent from each individual participating in this study after adequate explanation of the aims, methods, objectives, and potential hazards of the study and before undertaking any study-related procedures. The investigator must utilize an IRB/IEC-approved ICF for documenting written informed consent. Each ICF will be appropriately signed and dated by the patient or the patient's legally authorized representative and the person obtaining consent.

Informed consent will be obtained before the patient can participate in the study. The contents and process of obtaining informed consent will be in accordance with all applicable regulatory requirements.

11.2.4. Investigator Reporting Requirements

As indicated in [Section 9.5](#), the investigator (or sponsor, where applicable) is responsible for reporting SAEs to the IEC/IRB in accordance with all applicable regulations. Furthermore, the investigator may be required to provide periodic safety updates on the conduct of the study at his/her study center and notification of study closure to the IEC/IRB. Such periodic safety updates and notifications are the responsibility of the investigator and not of the sponsor.

11.2.5. Confidentiality

Information on maintaining patient confidentiality in accordance with individual local and national patient privacy regulations must be provided to each patient as part of the informed consent process, either as part of the ICF or as a separate signed document (for example, in the USA, a study center-specific HIPAA consent may be used). The investigator must ensure that patients' anonymity will be strictly maintained and that their identities are protected from unauthorized parties. Only patient initials, year of birth, and an identification code (ie, not names) should be recorded on any form or biologic sample submitted to the sponsor, IRB, or laboratory. The investigator must keep a screening log showing codes, names, and addresses for all patients screened and for all patients enrolled in the study.

The investigator agrees that all information received from BeiGene, including but not limited to the Investigator's Brochure, this protocol, eCRFs, the Investigational New Drug application, and any other study information, remain the sole and exclusive property of BeiGene during the conduct of the study and thereafter. This information is not to be disclosed to any third party (except employees or agents directly involved in the conduct of the study or as required by law) without prior written consent from BeiGene. The investigator further agrees to take all reasonable precautions to prevent the disclosure by any employee or agent of the study center to any third party or otherwise into the public domain.

11.2.6. Electronic Case Report Forms

For each patient enrolled, an eCRF must be completed and signed by the principal investigator or subinvestigator within a reasonable time period after data collection. This also applies to records for those patients who discontinue the study early. If a patient withdraws from the study, the reason must be noted on the eCRF. If a patient is withdrawn from the study because of a treatment-limiting AE, thorough efforts should be made to clearly document the outcome.

The eCRFs exist within an EDC system with controlled access managed by BeiGene or its authorized representative for this study. Study staff will be appropriately trained in the use of eCRFs and applications of electronic signatures before the study start and before being given access to the EDC system. Original data and any changes of data will be recorded using the EDC system, with all changes

tracked by the system and recorded in an electronic audit trail. The investigator attests that the information contained in the eCRFs is true by providing an electronic signature within the EDC system. After final database lock, the investigator will receive a copy of the patient data on CD-ROMs for archiving the data at the study center.

11.2.7. Drug Accountability

The investigator or designee (ie, pharmacist) is responsible for ensuring adequate accountability of all used and unused pamiparib. This includes acknowledgment of receipt of each shipment of pamiparib (quantity and condition), patient dispensing records, and returned or destroyed pamiparib. Dispensing records will document quantities received from BeiGene and quantities dispensed to patients, including lot number, date dispensed, patient identifier number, patient initials, and the initials of the person dispensing the medication.

At study initiation, the monitor will evaluate the study center's standard operating procedure for pamiparib disposal/destruction to ensure that it complies with BeiGene requirements specified in the Pharmacy Manual. At appropriate times during the conduct of the study or at the end of the study, following final drug inventory reconciliation by the monitor, the study center will dispose of and/or destroy all unused pamiparib supplies, including empty containers, according to these procedures. If the study center cannot meet BeiGene's requirements specified in the Pharmacy Manual for disposal, arrangements will be made between the study center and BeiGene or its representative for destruction or return of unused pamiparib supplies.

All drug supplies and associated documentation will be periodically reviewed and verified by the study monitor over the course of the study.

11.2.8. Inspections

The investigator should understand that source documents for this study should be made available to appropriately qualified personnel from BeiGene or its representatives, to IRBs/IECs, or to regulatory authority or health authority inspectors.

11.2.9. Protocol Adherence

The investigator is responsible for ensuring that the study is conducted in accordance with the procedures and evaluations described in this protocol. Investigators assert that they will apply due diligence to avoid protocol deviations.

11.3. Sponsor Responsibilities

11.3.1. Protocol Modifications

Protocol modifications, except those intended to reduce immediate risk to study patients, may be initiated only by BeiGene. All protocol modifications must be submitted to regulatory authorities and the IRB/IEC together with, if applicable, a revised model ICF in accordance with local requirements. As applicable by local requirements, written documentation of regulatory authorities, IRB/IEC, and required study center approval must be obtained by the sponsor before changes can be implemented.

Information on any change in risk and/or change in scope must be provided to patients already actively participating in the study, and they must read, understand, and sign each revised ICF confirming his/her willingness to remain in the study.

11.3.2. Use of Information and Publication

A clinical study report will be prepared and provided to the regulatory agency(ies) of participating countries. The sponsor will ensure that the report meets the standards set out in the International Council for Harmonisation Guideline for Structure and Content of Clinical Study Reports (ICH E3). Note that an abbreviated report may be prepared in certain cases.

The sponsor recognizes the importance of communicating medical study data, and therefore, encourages their publication in reputable scientific journals and at seminars or conferences. The details of the processes of producing and reviewing reports, manuscripts, and presentations based on the data from this study will be described in the clinical study agreement.

If a written contract for the conduct of the study, which includes publication provisions inconsistent with this statement, is executed, that contract's publication provisions shall apply rather than this statement.

11.4. Study and Study Center Closure

Upon completion of the study, the monitor will conduct the following activities in conjunction with the investigator or study center personnel, as appropriate:

- Return of all study data to the sponsor
- Data queries
- Accountability, reconciliation, and arrangements for unused pamiparib
- Review of study records for completeness
- Return of treatment codes to the sponsor
- Shipment of PK samples to assay laboratories

In addition, the sponsor reserves the right to temporarily suspend or prematurely discontinue this study either at a single study center or at all study centers at any time for reasons including but not limited to safety or ethical issues or severe noncompliance with this protocol, GCP, the clinical study agreement, or applicable laws and regulations. If the sponsor determines such action is needed, the sponsor will discuss this with the investigator (including the reasons for taking such action) at that time. When feasible, the sponsor will provide advance notification to the investigator of the impending action before it takes effect.

The sponsor will promptly inform all other investigators and/or institutions conducting the study if the study is suspended or terminated for safety reasons and will also inform the regulatory authorities of the suspension or termination of the study and the reason(s) for the action. If required by applicable

regulations, the investigator must inform the IEC/IRB promptly and provide the reason for the suspension or termination.

If the study is prematurely discontinued, all study data must still be provided to the sponsor. In addition, arrangements will be made for all unused pamiparib in accordance with the applicable sponsor procedures for the study.

Financial compensation to investigators and/or institutions will be in accordance with the agreement established between the investigator and the sponsor.

